5.1. Etigilimab Dose Holds and Discontinuation

Permanent Discontinuation Criteria for Etigilimab

Dosing with etigilimab should be permanently discontinued for the following toxicities:

- \geq Grade 4 neutropenia persisting for \geq 7 days and/or complicated by infection febrile neutropenia.
- \geq Grade 4 thrombocytopenia.
- Grade 3 drug-related thrombocytopenia $>$ 7 days or associated with clinically significant bleeding requires discontinuation.
- Any \geq Grade 3 non-hematologic toxicity, except:
 - Grade 3 fatigue lasting $<$ 7 days.
 - Grade 3 nausea, emesis, or diarrhea responding to supportive treatment within 5 days.
- Grade 3 drug-related AE of the skin requires dose discontinuation.
- \geq Grade 3 non-hematological laboratory abnormalities do not require treatment discontinuation except:
 - Grade \geq 3 AST, ALT, total bilirubin requires dose discontinuation
 - Concurrent AST or ALT $>$ 3 x ULN and total bilirubin $>$ 2 x ULN requires permanent dose discontinuation.

Note: In most cases of Grade 3 AST or ALT elevation, study treatment will be permanently discontinued. If the investigator determines a possible favorable benefit/risk ratio that warrants continuation of study treatment, a discussion between the investigator and the Medical Monitor or designee must occur.

- Isolated Grade 4 electrolyte imbalances/abnormalities that are not associated with clinical sequelae and are corrected with supplementation/appropriate management within 72 hours of their onset.

Etigilimab may be held/delayed due to toxicity. The dose level of etigilimab will not be modified for individual subjects in this study.

Dose Delay Criteria for Etigilimab

- Grade 2 non-skin, drug-related AE, except for fatigue.
- Grade 2 drug-related creatinine, AST, ALT, and/or total bilirubin abnormalities.
- Grade 3 skin drug-related AE.
- Grade 3 drug-related laboratory abnormality with the following exceptions:
 - Grade 3 lymphopenia or asymptomatic amylase or lipase does not require a dose delay.
- Any AE, laboratory abnormality or inter-current illness which, in the judgment of the investigator, warrants delaying the dose of study medication.

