The maximum duration of a dose hold is 28-days, unless a longer hold is approved by the Medical Monitor or designee; thereafter, the subject should be discontinued from etigilimab treatment. Etigilimab infusions may be delayed to allow subjects to recover from study treatment related AEs or intercurrent illness. Subjects who require delay of etigilimab should be re-evaluated weekly or more frequently if clinically indicated and resume etigilimab dosing when re-treatment criteria are met (see below) following discussion with the Medical Monitor. Individual subject cases should be discussed with the Sponsor Medical Monitor or designee for individual treatment decisions.

Dosing visits are not skipped, only delayed. Tumor assessments should continue as per protocol even if dosing is delayed.

Criteria to Resume Etigilimab Dosing

- Subjects will be permitted to resume etigilimab therapy following resolution of the AE to \leq Grade 1 or to baseline value, with the following exceptions.
- Subjects may resume treatment in the presence of Grade 2 fatigue.
- Subjects who have not experienced a Grade 3 drug-related skin AE may resume treatment in the presence of Grade 2 skin toxicity.
- For subjects with Grade 2 AST, ALT, and/or total bilirubin abnormalities, dosing may resume when laboratory values return to baseline and management with corticosteroids, if needed, is complete (See Appendix 8).
- Drug-related pulmonary toxicity, diarrhea, or colitis must have resolved to baseline before treatment is resumed. Subjects with persistent Grade 1 pneumonitis after completion of a steroid taper over at least 1 month may be eligible for retreatment if discussed with and approved by the Medical Monitor or designee.
- Subjects with drug-related endocrinopathies adequately controlled with only physiologic hormone replacement may resume treatment after consultation with the Medical Monitor or designee. Adrenal insufficiency requires discontinuation regardless of control with hormone replacement.

Subjects who meet criteria for permanent discontinuation must not receive further study therapy.

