5.2. Nivolumab Dose Hold, Resumption and Discontinuation

Nivolumab may be held/interrupted due to toxicity. The dose level of nivolumab will not be modified in this study. Repeat nivolumab infusions may be delayed to allow subjects to recover from study treatment related AEs or intercurrent illness. Dosing visits are not skipped, only delayed. Tumor assessments should continue as per protocol even if dosing is delayed.

A pattern of immune-related AEs has been defined for nivolumab treatment for which management algorithms have been developed ([OPDIVO 2018](#)). Most high- grade events were manageable with dose delays and the use of corticosteroids or hormone replacement therapy (endocrinopathies) as instructed in these algorithms.

Details on dose delays, re-initiation of treatment and discontinuation of nivolumab are provided below.

Dose Delay Criteria for Nivolumab

Nivolumab administration should be delayed for the following:

- Grade 2 non-skin, drug-related AE, except for fatigue.
- Grade 2 drug-related creatinine, AST, ALT and/or total bilirubin abnormalities.
- Grade 3 skin drug-related AE.
- Grade 3 drug-related laboratory abnormality with the following exceptions:
 - Grade 3 lymphopenia or asymptomatic amylase or lipase does not require a dose delay.
 - Grade ≥ 3 AST, ALT, total bilirubin required dose discontinuation (see below).
- Any AE, laboratory abnormality or inter-current illness which, in the judgment of the investigator, warrants delaying the dose of study medication.

Subjects who require delay of nivolumab should be re-evaluated weekly or more frequently if clinically indicated and resume nivolumab dosing when re-treatment criteria are met (see below).

If the decision is to resume nivolumab dosing, the subject should restart treatment on the next regularly scheduled dosing visit. Skipped doses are not to be replaced. If treatment is delayed >8 weeks, the subject may potentially be permanently discontinued from all study therapy, except as specified in the treatment discontinuation criteria below. Individual subject cases should be discussed with the Medical Monitor or designee for individual treatment decisions.

Criteria to Resume Nivolumab Dosing

Subjects will be permitted to resume nivolumab therapy following resolution of the AE to \leq Grade 1 or to baseline value, with the following exceptions:

- Subjects may resume treatment in the presence of Grade 2 fatigue.

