- k. Etigilimab must be dosed as described in the Protocol. Dosing of etigilimab should be within ± 2 days of the Study Day listed in the schedule of assessments. If etigilimab cannot be administered in this 2-day window, then that dose is considered missed. If treatment with etigilimab is delayed for >4 weeks, etigilimab will be permanently discontinued.
- l. Nivolumab must be dosed as described in the Protocol within ± 2 days of the Study Day listed in the schedule of assessments. If the etigilimab dose is delayed ± 2 days then the nivolumab dose would be delayed and administered on the same day as the etigilimab (except for C1D1 where etigilimab is administered without nivolumab).
- m. After initiation of study drug, report all adverse events until 90 days after the treatment termination visit.
- n. Thyroid function tests (TSH, free T3, and free T4) must be performed every 8 weeks or as clinically indicated and at treatment termination.
- o. Urinalysis (specific gravity, pH, glucose, protein, ketones, and blood) will be obtained during screening, at Study Days 22, 64, and at the time of treatment termination. Microanalysis is required if protein or blood is detected.
- p. Serum pregnancy test (for women of childbearing potential, including women who have had a tubal ligation) must be performed and documented as negative within 7 days prior to Cycle 1, Day 1 and at treatment termination.
- q. Perform tests for pertinent tumor markers (e.g., CEA for subjects with colorectal cancer or others) every 4 weeks or as needed starting at Cycle 1 Day 1.
- r. PK and ADA samples will be drawn according to [Table 3](#) listed below.

- s. A pre-dose sample of 33 mL will be drawn during screening and on Study Days, 1, 8, 22, and 36 and every 6 weeks after day 36 for subjects continuing on study drug to evaluate changes in plasma proteins (8 mL) by immunochemistry, TIGIT and immune-related gene expression by mRNA (5 mL) and changes in peripheral blood mononuclear cell (PBMC, 20 mL) populations and activation. A sample will also be collected at the time of treatment termination, unless one has been obtained during the prior 14 days. Instructions for the collection, handling, storage, and shipment are provided in the Laboratory Manual.
- t. A 6 mL of blood will be collected for pharmacogenetic testing if the subject has consented to have this optional sample collected.

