Patients on IV steroids may be switched to an equivalent dose of oral corticosteroids (e.g. prednisone) at start of tapering or earlier, once sustained clinical improvement is observed. Lower bioavailability of oral corticosteroids should be taken into account when switching to the equivalent dose of oral corticosteroids.

Myocarditis Adverse Event Management Algorithm

Patients on IV steroids may be switched to an equivalent dose of oral corticosteroids (eg, prednisone) at start of tapering or earlier, once sustained clinical improvement is observed. Lower bioavailability of oral corticosteroids should be taken into account when switching to the equivalent dose of oral corticosteroids.

Prophylactic antibiotics should be considered in the setting of ongoing immunosuppression.

ATG = anti-thymocyte globulin; BNP = B-type natriuretic peptide; ECG = electrocardiogram; IV = intravenous; MRI = magnetic resonance imaging

Additional Guidelines for Management of CTCAE-based immune-related hepatic adverse events (Puzanov 2017)

Hepatitis (AST, ALT and Total Bilirubin)		
Grade	CTCAE Description*	
1	AST, ALT >ULN -3xULN; total bilirubin >ULN-1.5xULN	
 Continue study drug Continue Liver function panel once weekly
2	AST, ALT >3- <5xULN; total bilirubin >1.5 - 3xULN	
 Hold study drug Rule out viral hepatitis, autoimmune disease, biliary obstruction, new metastasis or thrombosis Start prednisone 0.5-1 mg/kg/day (or equivalent dose of methylprednisolone) with 4 week taper Monitor liver function panel twice a week Liver biopsy is optional Resume study drug as per Section 5
3 and 4	AST, ALT >5xULN; total bilirubin >3xULN	
 Permanently discontinue Study Drug Monitor liver function panel every 1–2 days Start prednisone 1–2 mg/kg/day 
 If refractory after 3 days, consider mycophenolate If liver enzymes improve, taper corticosteroid over 4 weeks Consider liver biopsy

* https://ctep.cancer.gov/protocoldevelopment/electronic_applications/docs/ctcae_v5_quick_reference_5x7.pdf

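### Section 5.1 sends a drug-related Grade 3 AST/ALT rise to permanent stop, to dose delay and to possible continuation, other text bars further therapy, and the limit on etigilimab holds is stated inconsistently

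*Protocol*

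**What the plan says.** On a Grade 3 rise in AST or ALT, the protocol says the following.

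- **Section 5.1, stop list.** It opens with "Dosing with etigilimab should be permanently discontinued for the following toxicities". Grade 3 or higher AST, ALT or total bilirubin is one of the entries, and it is not limited to drug-related events.
- **Section 5.1, Note (repeated for nivolumab in Section 5.2).** Stopping for Grade 3 AST or ALT is described as what happens mostly, not always. The alternative begins "If the investigator determines a possible favorable benefit/risk ratio that warrants continuation of study treatment", and requires a discussion with the Medical Monitor or designee.
- **Section 5.1, delay list.** One bullet reads "Grade 3 drug-related laboratory abnormality with the following exceptions". The only exceptions are lymphopenia and asymptomatic amylase or lipase.
- **Section 5.2, delay list.** The same bullet carries an extra line, that Grade 3 or higher "AST, ALT, total bilirubin required dose discontinuation (see below").
- **Sections 5.1 and 5.2, end of the resume criteria.** "Subjects who meet criteria for permanent discontinuation must not receive further study therapy".
- **Appendix 8, hepatic table, Grades 3 and 4.** "Permanently discontinue Study Drug", with no exception in the row. The appendix opens by calling its content guidance that Medical Monitor discussion may supplement.
- **Section 5.1, resume criteria.** In general, dosing may resume at Grade 1 or lower, or at baseline. For Grade 2 liver values, the result must be back at baseline and "management with corticosteroids, if needed, is complete".

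On how long etigilimab may be held, Section 5.1 sets 28 days unless the Medical Monitor or designee approves longer. Section 7 withdraws a subject from treatment for a drug-related delay of more than 28 days. Note k of Section 8.1 says "If treatment with etigilimab is delayed for >4 weeks, etigilimab will be permanently discontinued". Neither of the last two mentions an extension.

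**The concern.** Whether to stop, hold or continue after a Grade 3 transaminase rise is a patient-safety decision. Two sites could handle the same laboratory value differently, each with protocol text on its side.

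Reporting is affected too. Section 8.8 requires the final report to summarise cases where therapy went on although it should have ended. A subject continued under the Note complies with the Note but breaches the sentence barring further therapy. A subject whose etigilimab hold was extended with approval complies with Section 5.1 but not with note k. The documents do not say how either case is to be classified.

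**Working it through.** The main point involves no arithmetic. For a **drug-related Grade 3 AST/ALT rise**, the instructions compare as follows.

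| Source | How it reaches the event | Instruction |
|---|---|---|
| 5.1 stop list | By name | Permanent discontinuation |
| 5.1 Note | By name (AST or ALT; not bilirubin) | Usually discontinue; continuation possible after discussion |
| 5.1 delay list | Through the general laboratory bullet, drug-related only | Delay |
| 5.1 and 5.2, end of resume criteria | Because a stop criterion is met | No further study therapy |
| Appendix 8 table | By threshold, above 5 x ULN | Permanent discontinuation, as guidance |

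1. *Stop list and Note.* The Note can be read as a deliberate exception to the stop entry. Taken alone, the two are compatible.
2. *Note and the bar on further therapy.* A Grade 3 rise meets a stop criterion by name. The Note does not say that a continued subject is exempt from the bar, and the bar mentions no exception.
3. *Delay list and stop list.* The same event sits in both. Section 5.2 addresses this overlap with its extra line; Section 5.1 has no such line.
4. *Discussion or approval.* The Note asks for a discussion. For persistent Grade 1 pneumonitis, the Section 5.1 resume criteria ask for discussion and approval, so the protocol does distinguish the two.
5. *Resuming.* If a Grade 3 rise is handled as a delay, the general criterion applies: Grade 1 or lower, **or** baseline, with no steroid condition. A Grade 2 rise needs baseline **and** completion of any steroid management. Every subject who meets the Grade 2 condition meets the general one, but not the reverse. On this route the more severe event has the looser restart condition.

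**Hold limit.** The Appendix 8 Grade 2 row prescribes a 4 week taper: 4 x 7 = 28 days. Assume that the taper starts when the rise is found and that the delay counts from the first withheld dose.

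- Rise found on a dosing day (from Cycle 7 the only scheduled safety-laboratory days, note w): delay 28 days, margin 28 - 28 = 0 days.
- Rise found 7 days before a due dose: delay 28 - 7 = 21 days, margin 28 - 21 = 7 days.

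Neither case exceeds a limit of more than 28 days. Steroid treatment before the taper begins, or a slower return to baseline, uses up the margin. Past that point Section 5.1 allows an approved extension, while Section 7 and note k do not provide for one.

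**Is the event foreseeable?** Section 1.2 reports Grade 3 or higher ALT in 2/23 = 8.7% on etigilimab alone and Grade 3 or higher AST in 2/10 = 20.0% on the combination. These are laboratory results, not limited to drug-related events.

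**The case against.** The strongest reply is that the text works if read sensibly. The delay bullet is generic and does not name AST or ALT, so the specific stop entry should prevail. The Note is then a controlled exception. Appendix 8 is guidance open to supplement by Medical Monitor discussion, which is what the Note requires. The Appendix 8 point stands: the tension between the Note and that table is mild. Its hepatic algorithm figure is also not available in the text reviewed, so only the table could be compared. The rest does not resolve Section 5.1. No rule says that specific entries override general ones, and nothing squares the Note with the bar on further therapy.

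Three stronger readings are tempting but unsupported.

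- *A Grade 3 rise has no hold, recheck or restart rule.* If it is handled as a delay, the delay list, weekly re-evaluation and the general resume criterion all reach it. Appendix 8 asks for a liver panel every 1 to 2 days at Grades 3 and 4. What is missing is narrower: the Note does not say which of these apply to a subject continued under it.
- *The Grade 2 path cannot be completed in time.* A 28-day taper does not itself exceed the limit, steroids are conditional on need, and Section 5.1 allows a longer approved hold. For nivolumab, Section 5.2 uses an 8-week threshold and allows interruptions for prolonged tapers. The supported point is the mismatch in etigilimab limits.
- *The SAP's Table 14.3.1.1 counts of doses held and discontinued would reflect site reading rather than toxicity.* Nothing shows how often readings would differ, and Listing 16.2.7 gives the grade and the action taken on each drug for every event.

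**Conclusion.** The concern holds as a wording conflict on a safety decision. For a drug-related Grade 3 AST/ALT rise, the Section 5.1 instructions cannot all be followed, and deviation classification under Section 8.8 is ambiguous as a result. The looser restart condition for Grade 3 than for Grade 2 arises only if the delay route is taken. The difference in etigilimab hold limits is a separate, smaller inconsistency.

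Its size cannot be put as a number of subjects. A reader might scale the earlier rates to the planned 125 enrolled: 125 x 2/23 = 10.9 and 125 x 2/10 = 25. That is not supported. The two rates concern different tests on different regimens, include grades above 3, and are not limited to drug-related events. They are also very imprecise, with exact 95% intervals of 1.1% to 28.0% and 2.5% to 55.6%. They show that the event is foreseeable, no more.

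Section 6.3 of the SAP records that the study was terminated, so 125 is only the planned number, and new wording may affect few subjects still on treatment. It would still matter for classifying deviations and for any reuse of this text.

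**What to change.** Reconcile Sections 5.1 and 5.2 (stop lists, Notes, delay lists and resume criteria) and the Appendix 8 hepatic table, so that one consistent rule for Grade 3 or higher AST, ALT and total bilirubin appears throughout. The reconciled text should state whether the Note's exception exists and, if so, how it operates against the sentence barring further study therapy and which hold and resume criteria then apply.

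Reconcile the etigilimab hold limits in Section 5.1, Section 7 and note k of Section 8.1, including whether an approved extension is available where the Appendix 8 taper is used.

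The sponsor's clinical team decides which rules stand; this review takes no position on that. The cost is protocol wording and a site clarification, with no added visits.

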5.2. Nivolumab Dose Hold, Resumption and Discontinuation

Nivolumab may be held/interrupted due to toxicity. The dose level of nivolumab will not be modified in this study. Repeat nivolumab infusions may be delayed to allow subjects to recover from study treatment related AEs or intercurrent illness. Dosing visits are not skipped, only delayed. Tumor assessments should continue as per protocol even if dosing is delayed.

A pattern of immune-related AEs has been defined for nivolumab treatment for which management algorithms have been developed ([OPDIVO 2018](#)). Most high- grade events were manageable with dose delays and the use of corticosteroids or hormone replacement therapy (endocrinopathies) as instructed in these algorithms.

Details on dose delays, re-initiation of treatment and discontinuation of nivolumab are provided below.

Dose Delay Criteria for Nivolumab

Nivolumab administration should be delayed for the following:

- Grade 2 non-skin, drug-related AE, except for fatigue.
- Grade 2 drug-related creatinine, AST, ALT and/or total bilirubin abnormalities.
- Grade 3 skin drug-related AE.
- Grade 3 drug-related laboratory abnormality with the following exceptions:
 - Grade 3 lymphopenia or asymptomatic amylase or lipase does not require a dose delay.
 - Grade ≥ 3 AST, ALT, total bilirubin required dose discontinuation (see below).
- Any AE, laboratory abnormality or inter-current illness which, in the judgment of the investigator, warrants delaying the dose of study medication.

Subjects who require delay of nivolumab should be re-evaluated weekly or more frequently if clinically indicated and resume nivolumab dosing when re-treatment criteria are met (see below).

If the decision is to resume nivolumab dosing, the subject should restart treatment on the next regularly scheduled dosing visit. Skipped doses are not to be replaced. If treatment is delayed >8 weeks, the subject may potentially be permanently discontinued from all study therapy, except as specified in the treatment discontinuation criteria below. Individual subject cases should be discussed with the Medical Monitor or designee for individual treatment decisions.

Criteria to Resume Nivolumab Dosing

Subjects will be permitted to resume nivolumab therapy following resolution of the AE to \leq Grade 1 or to baseline value, with the following exceptions:

- Subjects may resume treatment in the presence of Grade 2 fatigue.
- Subjects who have not experienced a Grade 3 drug-related skin AE may resume treatment in the presence of Grade 2 skin toxicity.

- For subjects with Grade 2 AST, ALT, and/or total bilirubin abnormalities, dosing may resume when laboratory values return to baseline and management with corticosteroids, if needed, is complete.
- Drug-related pulmonary toxicity, diarrhea or colitis must have resolved to baseline before treatment is resumed. Subjects with persistent Grade 1 pneumonitis after completion of a steroid taper over at least 1 month may be eligible for retreatment if discussed with and approved by the Medical Monitor or designee.
- Subjects with drug-related endocrinopathies adequately controlled with only physiologic hormone replacement may resume treatment after consultation with the Medical Monitor or designee. Adrenal insufficiency requires discontinuation regardless of control with hormone replacement.
- Subjects who meet criteria for permanent discontinuation must not receive further study therapy.

Permanent Treatment Discontinuation Criteria for Nivolumab

Subjects meeting any of the following criteria will be required to permanently discontinue nivolumab:

- Any Grade 2 drug-related uveitis or eye pain or blurred vision that does not respond to topical therapy and does not improve to Grade 1 severity within 8 weeks OR requires systemic treatment.
- Any Grade 3 non-skin, drug-related AE lasting >7 days or recurs, with the following exceptions for laboratory abnormalities, drug-related uveitis, pneumonitis, bronchospasm, neurologic toxicity, hypersensitivity reactions, infusion reactions, and endocrinopathies:
 - Grade 3 drug-related uveitis, pneumonitis, bronchospasm, neurologic toxicity, myocarditis, hypersensitivity reaction, or infusion reaction **of any duration** requires discontinuation.
 - Grade 3 drug-related endocrinopathies adequately controlled with only physiologic hormone replacement do not require discontinuation. Adrenal insufficiency requires discontinuation regardless of control with hormone replacement.
- Grade 3 drug-related laboratory abnormalities do not require treatment discontinuation except:
 - Grade 3 drug-related thrombocytopenia >7 days or associated with clinically significant bleeding requires discontinuation.
 - Grade ≥ 3 drug-related AST, ALT, or total bilirubin requires discontinuation.
 - Concurrent AST or ALT $>3 \times$ ULN and total bilirubin $>2 \times$ ULN.
 - In most cases of Grade 3 AST or ALT elevation, study treatment will be permanently discontinued. If the investigator determines a possible favorable benefit/risk ratio that warrants continuation of study treatment, a discussion between the investigator and the Medical Monitor or designee must occur.

- Any Grade 4 drug-related AE or laboratory abnormality (including but not limited to creatinine, AST, ALT, or total bilirubin), except for the following events, which do not require discontinuation:
 - Grade 4 neutropenia \leq 7 days.
 - Grade 4 lymphopenia or leukopenia or asymptomatic amylase or lipase.
 - Isolated Grade 4 electrolyte imbalances/abnormalities that are not associated with clinical sequelae and are corrected with supplementation/appropriate management within 72 hours of their onset.
 - Grade 4 drug-related endocrinopathy AEs such as hyper- or hypothyroidism, or glucose intolerance, which resolve or are adequately controlled with physiologic hormone replacement (corticosteroids, thyroid hormones) or glucose-controlling agents, respectively, may not require discontinuation after discussion with and approval from the Medical Monitor or designee.
- Any AE, laboratory abnormality, or intercurrent illness, which, in the judgment of the investigator, presents a substantial clinical risk to the subject with continued treatment.

Criteria for Further Discussion with Medical Monitor or Designee Before Deciding to Continue or Discontinue Nivolumab Treatment

For subjects meeting any of the following criteria, discussion with the Medical Monitor or designee is to occur to determine whether treatment should continue. Any dosing interruption of nivolumab lasting >8 weeks after the last dose. Dosing interruptions to allow for prolonged steroid tapers to manage drug- related AEs are allowed. Prior to re-initiating treatment in a subject with a dosing interruption lasting >8 weeks after the last dose and with no more than 2 missed doses, the Medical Monitor or designee must be consulted. Tumor assessments should continue as per protocol even if dosing is interrupted.

